9.1. Estimands and Statistical Hypotheses

9.1.1. Estimands

The estimands corresponding to each primary, secondary, CCI objective are described in the table in Section 3. The estimands to evaluate the immunogenicity objectives for NI) are based on the evaluable populations (see Section 9.3 for definition). The estimands estimate the vaccine effect in the hypothetical setting where participants follow the study schedules and protocol requirements as directed. The estimands address the objective of estimating the maximum potential difference between 2 groups, since the impact of noncompliance is likely to diminish the observed difference between the 2 groups. Missing serology results will not be imputed. Immunogenicity results that are below the LLOQ will be set to $0.5 \times \text{LLOQ}$ in the analysis. In the primary safety objective evaluations, missing e-diary data will not be imputed. Missing AE dates will be imputed according to Pfizer Safety rules. No other missing information will be imputed in the safety analysis.

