9.2. Sample Size Determination

CCI

Sample size and power are based on simulations with assumptions supported by the OPA results from a Phase 3 pivotal study (B7471007) of 20vPnC and a Phase 4 study (B1851138) of 13vPnC evaluating the immune response when 13vPnC was given concomitantly and separately. With 800 evaluable participants in each vaccine group, the study has approximately 99%, 95%, and 75% power to demonstrate NI for at least 18 out of 20, for at least 19 out of 20, and for all 20 serotypes, respectively. Assuming a nonevaluable rate of 10%, the study will randomize approximately 1780 participants to achieve 800 evaluable participants in each group.

CCI

[REDACTED]

[REDACTED]	[REDACTED]	+	[REDACTED]
[REDACTED]	[REDACTED]	[REDACTED]	[REDACTED]
[REDACTED]	[REDACTED]	[REDACTED]	[REDACTED]
[REDACTED]	[REDACTED]	[REDACTED]	[REDACTED]
[REDACTED]	[REDACTED]	[REDACTED]	[REDACTED]
[REDACTED]	[REDACTED]	[REDACTED]	[REDACTED]
[REDACTED]	[REDACTED]	[REDACTED]	[REDACTED]
[REDACTED]	[REDACTED]	[REDACTED]	[REDACTED]
[REDACTED]	[REDACTED]	[REDACTED]	[REDACTED]
[REDACTED]	[REDACTED]	[REDACTED]	[REDACTED]
[REDACTED]	[REDACTED]	[REDACTED]	[REDACTED]
[REDACTED]	[REDACTED]	[REDACTED]	[REDACTED]
[REDACTED]	[REDACTED]	[REDACTED]	[REDACTED]
[REDACTED]	[REDACTED]	[REDACTED]	[REDACTED]
[REDACTED]	[REDACTED]	[REDACTED]	[REDACTED]
[REDACTED]	[REDACTED]	[REDACTED]	[REDACTED]
[REDACTED]	[REDACTED]	[REDACTED]	[REDACTED]
[REDACTED]	[REDACTED]	[REDACTED]	[REDACTED]
[REDACTED]	[REDACTED]	[REDACTED]	[REDACTED]
[REDACTED]	[REDACTED]	[REDACTED]	[REDACTED]
[REDACTED]	[REDACTED]	[REDACTED]	[REDACTED]
[REDACTED]	[REDACTED]	[REDACTED]	[REDACTED]
[REDACTED]	[REDACTED]	[REDACTED]	[REDACTED]
[REDACTED]	[REDACTED]	[REDACTED]	[REDACTED]
[REDACTED]	[REDACTED]	[REDACTED]	[REDACTED]
[REDACTED]	[REDACTED]	[REDACTED]	[REDACTED]
[REDACTED]	[REDACTED]	[REDACTED]	[REDACTED]
[REDACTED]	[REDACTED]	[REDACTED]	[REDACTED]
[REDACTED]	[REDACTED]	[REDACTED]	[REDACTED]
[REDACTED]	[REDACTED]	[REDACTED]	[REDACTED]
[REDACTED]	[REDACTED]	[REDACTED]	[REDACTED]
[REDACTED]	[REDACTED]	[REDACTED]	[REDACTED]
[REDACTED]	[REDACTED]	[REDACTED]	[REDACTED]
[REDACTED]	[REDACTED]	[REDACTED]	[REDACTED]
[REDACTED]	[REDACTED]	[REDACTED]	[REDACTED]
[REDACTED]	[REDACTED]	[REDACTED]	[REDACTED]
[REDACTED]	[REDACTED]	[REDACTED]	[REDACTED]
[REDACTED]	[REDACTED]	[REDACTED]	[REDACTED]
[REDACTED]	[REDACTED]	[REDACTED]	[REDACTED]
[REDACTED]	[REDACTED]	[REDACTED]	[REDACTED]
[REDACTED]	[REDACTED]	[REDACTED]	[REDACTED]

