9.3. Analysis Sets

Participant Analysis Set	Description
Enrolled	All participants who sign the ICD.
Randomized	All participants who are assigned a randomization number in the IWR system.
Evaluable pneumococcal immunogenicity	All randomized participants who receive the assigned investigational products at Visit 1 for the (SIIV+20vPnC)/saline group or receive the assigned investigational products at both Visit 1 and Visit 2 for the (SIIV+saline)/20vPnC group; have the blood collection within an appropriate window 1 month after 20vPnC (Visit 2 for [SIIV+20vPnC]/saline group, Visit 3 for [SIIV+saline]/20vPnC group); have at least 1 valid and determinate OPA result from 1 month after vaccination with 20vPnC; and have no other major protocol deviations as determined by the clinician.
Evaluable HAI immunogenicity	All randomized participants who receive the assigned investigational products at Visit 1, have Visit 2 blood collection within an appropriate window for Visit 2, have at least 1 valid and determinate HAI titer for any of the HAI strains in SIIV at Visit 2, and have no other major protocol deviations as determined by the clinician.
CCI [REDACTED]	[REDACTED]
Safety	All randomized participants who receive 1 dose of 20vPnC or SIIV or saline and have safety follow-up after vaccination.

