Secondary pneumococcal immunogenicity	
• GMFRs and associated 2-sided 95% CIs will be provided for each OPA serotype from before vaccination to 1 month after vaccination for each vaccine group. GMFRs will be limited to participants with nonmissing values both before and after vaccination. The GMFR will be calculated as the mean of the difference of logarithmically transformed serotype-specific OPA titer (after vaccination minus before vaccination for each participant) and transformed back to the original units. 2-Sided 95% CIs will be obtained by exponentiating CIs using Student's t distribution for the mean difference of measures on the logarithmically transformed assay results.• The point estimate and exact 2-sided 95% CI will be calculated for each vaccine group using the Clopper-Pearson method for the percentage of participants with a ≥ 4-fold rise in serotype-specific OPA titers from before vaccination to 1 month after vaccination.
Secondary SIIV immunogenicity	
• HAI GMFRs and associated 2-sided 95% CIs will be provided for each HAI strain from before vaccination to 1 month after vaccination for each vaccine group, using the same method described above for serotype-specific OPA GMFRs and CIs.
CCI [REDACTED]	[REDACTED]
[REDACTED]	[REDACTED]

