3.1.2. Primary Pneumococcal Immunogenicity Endpoint

- Pneumococcal serotype-specific OPA titers 1 month after vaccination with 20vPnC.

OPA titers for the 20 pneumococcal serotypes (1, 3, 4, 5, 6A, 6B, 7F, 8, 9V, 10A, 11A, 12F, 14, 15B, 18C, 19A, 19F, 22F, 23F, and 33F) will be determined for all participants' sera collected at Visit 1 (prior to administration of SIIV and blinded vaccine), Visit 2 (1 month after administration of vaccines at Visit 1, and prior to blinded vaccine at Visit 2), and Visit 3 (1 month after vaccination at Visit 2).

OPA titers above the LLOQ are considered accurate and their quantitated values will be reported. OPA titers below the corresponding LLOQ or denoted as BLQ will be set to $0.5 \times$ LLOQ for analysis. Missing assay results will not be imputed.

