4. ANALYSIS SETS (POPULATIONS FOR ANALYSIS)

Analysis populations are defined for the statistical analysis of safety and immunogenicity results in the table below. For the specified criteria in each population definition that are not associated with unblinded information (randomized or actual received vaccination), data for all participants will be assessed to determine if participants meet the criteria for inclusion in each analysis population prior to unblinding and releasing the database for the specified analysis, and the classifications will be documented per standard operating procedures.

Population	Description
Enrolled	All participants who sign the ICD.
Randomized	All participants who are assigned a randomization number in the IWR system.
Evaluable pneumococcal immunogenicity	All randomized participants who 
 receive the assigned investigational products at Visit 1 for the (SIIV+20vPnC)/saline group or receive the assigned investigational products at both Visit 1 and Visit 2 for the (SIIV+saline)/20vPnC group have the blood collection within 27 to 49 days after 20vPnC (Visit 2 for the [SIIV+20vPnC]/saline group, Visit 3 for the [SIIV+saline]/20vPnC group) have at least 1 valid OPA result from the blood sample collected 1 month after vaccination with 20vPnC have no other major protocol deviations as determined by the clinician
Evaluable HAI immunogenicity	All randomized participants who 
 receive the assigned investigational products at Visit 1 have the Visit 2 blood collection within 27 to 49 days after vaccination with SIIV have at least 1 valid HAI titer for any of the HAI strains in SIIV at Visit 2

Population	Description
	
 have no other major protocol deviations as determined by the clinician

 

	CCI 

Safety	All randomized participants who receive 1 dose of 20vPnC or SIIV or saline and have safety follow-up after any dose.

The statistical analysis of immunogenicity results will be primarily based on the evaluable immunogenicity populations, ie, the evaluable pneumococcal immunogenicity population for OPA titers and the evaluable HAI immunogenicity population for HAI titers.

CCI

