5.2.2.2. Geometric Mean Ratios

Model-Based GMR

As the primary approach to calculate the GMR and CI for each serotype of OPA titer 1 month after 20vPnC, a linear regression model that includes terms for prior pneumococcal vaccine status, age at vaccination at Visit 1, corresponding baseline OPA titer, sex, smoking status, and vaccine group will be used to calculate the serotype-specific OPA GMR and the associated 95% CI, along with the model-based LS GMTs and associated 2-sided 95% CIs for each vaccine group.

As the primary approach to calculate the GMR and CI for each strain of HAI titer 1 month after SIIV, a linear regression model that includes terms for prior pneumococcal vaccine status, age at vaccination at Visit 1, corresponding baseline HAI titer, sex, smoking status, and vaccine group will be used to calculate the strain-specific HAI GMR and the associated 95% CI, along with the model-based LS GMTs and associated 2-sided 95% CIs for each vaccine group.

CCI [REDACTED]

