5.3. Methods to Manage Missing Data

A partial AE start date (missing day, missing both month and day) will be imputed by assigning the earliest possible start date using all available information, such as the stop date of the AE and the vaccination date(s) from the same participant, following the Pfizer standard of handling incomplete AE start date. A complete missing start date for an AE is not allowed in the data collection. No additional imputation will be applied unless stated otherwise (see [Section 3](#)).

The LLOQ for each assay will be provided by Vaccine Research & Development as part of the electronic data transfer or within the Clinical Testing Completion Memo prior to any statistical analysis of immunogenicity data. Assay results above the LLOQ will be reported, and values below the LLOQ, denoted as BLQ, will be set to $0.5 \times \text{LLOQ}$ for analysis.

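### Do the primary OPA and HAI models lose power because they adjust for a baseline titer that the evaluable populations do not require?

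*SAP*

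**What the plan says.** The primary OPA analysis (SAP 5.2.2.2 and 6.1.2.1, Protocol 9.4.1) is a "linear regression model that includes terms for prior pneumococcal vaccine status, age at vaccination at Visit 1, corresponding baseline OPA titer". Vaccine group, smoking status and sex complete it, and it is fitted separately for each of the 20 serotypes. SAP 6.1.2.2 gives each HAI strain the same model with its own baseline HAI titer.

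The evaluable populations look only at the post-vaccination side. For OPA, SAP section 4 asks that participants "have at least 1 valid OPA result from the blood sample collected 1 month after vaccination with 20vPnC". For HAI, Protocol 9.3 asks that they "have at least 1 valid and determinate HAI titer for any of the HAI strains in SIIV at Visit 2". Neither definition mentions a Visit 1 result.

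On missing data, Protocol 9.1.1 says "Missing serology results will not be imputed", SAP 3.1.2 says "Missing assay results will not be imputed", and SAP 5.3 adds "No additional imputation will be applied unless stated otherwise". Titers below the LLOQ are not missing; they are set to half the LLOQ. For the secondary fold rises, Protocol 9.4.1 gives an explicit pairing rule: "GMFRs will be limited to participants with nonmissing values both before and after vaccination". No matching sentence is visible for the primary models.

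Power is stated in Protocol 9.2: "With 800 evaluable participants in each vaccine group, the study has approximately 99%, 95%, and 75% power to demonstrate NI". The three figures refer to at least 18, at least 19 and all 20 serotypes respectively. Under Protocol 9.1.3, success requires all 20 serotypes and every HAI strain.

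**The concern.** A linear regression cannot use a record whose covariate is missing. A participant who meets the evaluable definition and has a valid primary outcome therefore drops out of any model for which the baseline titer is absent or indeterminate. The analysed set then differs from the named population and may vary by serotype.

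The sample size leaves almost no slack for this. The 10% allowance covers nonevaluable participants, and a participant without a baseline titer can still be evaluable. With about 75% power for all 20 serotypes, any further loss of information appears to matter. Because the pairing rule is written out for a secondary endpoint and not for the primary one, it also looks like an oversight that leaves a choice open until analysis.

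**Working it through.** **Inputs.** From the documents: 1780 randomized, 10% nonevaluable, 800 per group, power 99/95/75% for OPA and 99% for all HAI strains, HAI GMR 0.9, HAI margin 0.67. Not visible: the OPA GMRs, all SDs, the rate of missing baselines, the baseline-to-post correlation r of ln titers, and whether the simulations assumed baseline adjustment. Values for these are assumed below.

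**1. The plan's own figure.** 1600 / 0.9 = 1778, which matches the stated 1780 after rounding. Per group, 890 × 0.9 = 801. Two or more missing baselines in a group would take that model below 800.

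**2. Loss if the stated power already assumes adjustment.** Let m serotypes limit power, each at p = 0.75^(1/m), and let a fraction f be lost from every model. Then power for all 20 = Φ((1.96 + z(p))·√(1−f) − 1.96)^m.

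- Example, m = 1, f = 5%: (1.96 + 0.674) × 0.9747 − 1.96 = 0.608, and Φ = 0.728.
- Example, m = 20, f = 5%: (1.96 + 2.189) × 0.9747 − 1.96 = 2.084, and Φ^20 = 0.687.

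| f | m = 1 | m = 20 | Points lost |
|---|---|---|---|
| 1% | 74.6% | 73.8% | 0.4 to 1.2 |
| 2% | 74.1% | 72.6% | 0.9 to 2.4 |
| 5% | 72.8% | 68.7% | 2.2 to 6.3 |

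These figures treat limiting serotypes as independent. They also count any lost pre/post pair, including missing outcomes, so the share due to missing baselines alone is smaller. A nonevaluable rate slightly under 10% would offset the loss: 1 − 800/((1−f) × 890) = 9.2%, 8.3% and 5.4% for f = 1%, 2% and 5%.

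**3. HAI.** ln(0.9/0.67) = 0.295. Solving for the SD that gives 99% at 800 per group yields 1.24 (four equal independent strains) to 1.38 (one limiting strain). At 5% loss, power for all strains is 98.6 to 98.7%, a drop of less than 0.5 point.

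**4. If the stated power rests on unadjusted SDs.** Relative to the unadjusted analysis at full N, the complete-case adjusted variance is (1−r²)/(1−f). This is below 1 whenever r > √f, that is r above 0.10, 0.14 and 0.22 for f = 1%, 2% and 5%. At r = 0.3 and f = 5% it is 0.91/0.95 = 0.958. Using 1/0.958 in place of (1−f) in step 2 gives power of 76.8% (m = 1) to 79.7% (m = 20), above the stated 75%.

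**5. Would filling in the baseline do better?** Setting a missing baseline to the stratum mean pooled over groups gives relative variance (1−f)(1−r²) + f, against (1−r²)/(1−f) for complete case. With f = 2%:

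- r = 0.5: 0.755 against 0.765, so the SE is about 0.7% narrower with filling.
- r = 0.8: 0.373 against 0.367, so the SE is about 0.7% wider with filling.

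Break-even is at r = 0.709 to 0.716 for f = 1 to 5%.

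**6. Is complete case biased?** Protocol 8.1.1 and 8.11.1 require the baseline draw from everyone before vaccination, and Protocol 6.3.3 keeps the assay laboratory blinded. Absence of a baseline result should therefore not depend on vaccine group. A regression restricted to participants with a baseline is also not biased by absence that depends on the baseline titer itself.

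**The case for a change.** The strongest case for acting is that the gap is real and cheap to close. The analysed set can differ from the population named for the primary analysis, the design has one participant per group to spare, and a rule fixed before unblinding removes any discretion over 24 co-required tests (20 serotypes and four strains). A pooled-stratum fill uses no treatment information, imputes no outcome, and recovers about 90% of the lost information at r = 0.3 and 67% at r = 0.5.

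The factual part stands: the evaluable definitions do not secure a baseline, and the primary sections do not spell out the pairing rule. The rest is weaker. The no-imputation rule is repeated under both primary analyses (SAP 6.1.2.1 and 6.1.2.2), and together with a baseline covariate it leaves complete case as the natural reading, so little discretion remains. A skipped baseline draw could also be judged a major protocol deviation by the clinician and so fall within the 10%, although neither document says this. Redacted text follows the model descriptions and may hold supporting analyses. A varying N per serotype would remain under any fill, because one valid result for any serotype is enough to be evaluable. Filling would override the stated rule, might require a protocol amendment, and gains nothing once r exceeds about 0.71.

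**Conclusion.** No change follows. The plan has a small gap in wording that an analyst would fill sensibly: fit each primary model to participants with both the baseline and the post-vaccination titer, and show the N for each model in the table. Followed that way, the plan gives a sound comparison of the groups.

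A power shortfall is not shown. On the less favourable assumption (adjustment already built into the 75%), a 1 to 2% loss costs 0.4 to 2.4 points on a figure that the protocol itself calls approximate. On the other assumption, adjustment more than pays for a 5% loss at a correlation of only 0.3. HAI power is essentially unaffected. Everything beyond the 1778 and 801 rests on assumed missing rates and correlations and on normal approximations. Changing the method to fill in baselines would be a trade-off whose direction depends on a correlation the documents do not give.

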5.2.2.3. Geometric Mean Fold Rises

The GMFRs will be calculated as the mean of the difference of logarithmically transformed assay results (later minus earlier) and exponentiating back to the original units. The associated 2-sided 95% CIs will be computed by exponentiating the CIs using Student's t-distribution for the mean difference on the natural log scale.

CCI [REDACTED]

5.3. Methods to Manage Missing Data

A partial AE start date (missing day, missing both month and day) will be imputed by assigning the earliest possible start date using all available information, such as the stop date of the AE and the vaccination date(s) from the same participant, following the Pfizer standard of handling incomplete AE start date. A complete missing start date for an AE is not allowed in the data collection. No additional imputation will be applied unless stated otherwise (see [Section 3](#)).

The LLOQ for each assay will be provided by Vaccine Research & Development as part of the electronic data transfer or within the Clinical Testing Completion Memo prior to any statistical analysis of immunogenicity data. Assay results above the LLOQ will be reported, and values below the LLOQ, denoted as BLQ, will be set to $0.5 \times \text{LLOQ}$ for analysis.

6. ANALYSES AND SUMMARIES

6.1. Primary Endpoints

6.1.1. Primary Safety Endpoints

6.1.1.1. Prompted Local Reactions

Prompted local reactions after each vaccination of 20vPnC or saline at Visit 1 and Visit 2 will be summarized separately.

6.1.1.1.1. Main Analysis

- Estimand: The percentage of participants reporting prompted local reactions (redness, swelling, and pain at the injection site) within 10 days after vaccination ([Section 2.1](#)).
- Analysis set: Safety population ([Section 4](#)).
- Analysis time point: Within 10 days after each vaccination.
- Analysis methodology: Descriptive statistics. The between-group difference and the corresponding 2-sided 95% CI will be calculated using the Miettinen and Nurminen method ([Section 5.2.1](#)).
- Intercurrent events and missing data: Missing values will not be imputed. CCI [REDACTED]
- Reporting results: Count and percentage of participants with the indicated endpoint and the associated 2-sided 95% Clopper-Pearson CI for each and any local reaction after vaccination in each vaccine group will be presented by maximum severity level. Between-group differences (see [Section 5.2.1](#)) in these percentages and their 2-sided 95% CIs will also be provided.

CCI [REDACTED]

[REDACTED]

[REDACTED]

[REDACTED]

[REDACTED]

[REDACTED]

CCI [REDACTED]

[REDACTED]

[REDACTED]

[REDACTED]

6.1.1.2. Prompted Systemic Events

Prompted systemic events after each vaccination (vaccination at Visit 1 and vaccination at Visit 2) will be summarized separately.

6.1.1.2.1. Main Analysis

Estimand: The percentage of participants reporting prompted systemic events (fever, headache, fatigue, muscle pain, and joint pain) within 7 days after vaccination ([Section 2.1](#)).

- Analysis set: Safety population ([Section 4](#)).
- Analysis time point: Within 7 days after each vaccination.
- Analysis methodology: Descriptive statistics. The between-group difference and the corresponding 2-sided 95% CI will be calculated using the Miettinen and Nurminen method ([Section 5.2.1](#)).
- Intercurrent events and missing data: Missing values will not be imputed. CCI [REDACTED]
- Reporting results: Count and percentage of participants with the indicated endpoint and the associated 2-sided Clopper-Pearson 95% CI for each and any systemic event after vaccination in each vaccine group will be presented by maximum severity levels. Between-group differences (see [Section 5.2.1](#)) in these percentages and their 2-sided 95% CIs will also be provided.

CCI [REDACTED]

[REDACTED]

[REDACTED]

[REDACTED]

[REDACTED]

CCI [REDACTED]

[REDACTED]

[REDACTED]

[REDACTED]

6.1.1.3. Adverse Events

AEs after each vaccination (vaccination at Visit 1 and vaccination at Visit 2) will be summarized separately.

6.1.1.3.1. Main Analysis

- Estimands:
 - The percentages of participants reporting AEs within 1 month after vaccination at Visit 1 ([Section 2.1](#)).
 - The percentages of participants reporting AEs within 1 month after vaccination at Visit 2 ([Section 2.1](#)).
- Analysis set: Safety population ([Section 4](#)).
- Analysis time point: Within 1 month after each vaccination.
- Analysis methodology: 3-Tiered approach as described in [Section 5.2.1](#).
- Intercurrent events and missing data: No missing values will be imputed except for partial AE start dates ([Section 5.3](#)).
- Reporting results: For all 3 tiers, the numerator (n) and the denominator (N) used in the percentage calculation, the percentage (%), and the corresponding 2-sided 95% Clopper-Pearson CI for participants reporting any AE, each system organ class, and each preferred term within system organ class will be presented by vaccine group.

In addition, for AEs classified as Tier 2 events, the between-group difference and 95% CIs will be calculated for 1 month after SIIV and 20vPnC for the (SIIV+20vPnC)/saline group vs 1 month after SIIV and saline for the (SIIV+saline)/20vPnC group, and for 1 month after SIIV and 20vPnC for the (SIIV+20vPnC)/saline group vs 1 month after 20vPnC for the (SIIV+saline)/20vPnC group.

Further, for Tier 1 events, if any are identified, the difference in percentages, the associated 2-sided 95% CI for the risk differences (as described for Tier 2 events), and the asymptotic p-values will also be provided.

If any nonserious AEs are reported to occur before vaccination at Visit 1 or between 1 month after the last vaccination received in the group and the 6-month follow-up (between Visit 3 and Visit 4) (outside of the protocol-specified reporting window), they will not be summarized but will be included in the AE listings.

CCI [REDACTED]

[REDACTED]

[REDACTED]

[REDACTED]

